9.3 MULTIPLICITY

There are three sources of multiplicity in this study: multiplicity due to interim analyses, multiplicity due to multiple doses, and multiplicity due to multiple endpoints.

The overall type 1 error rate for the study is protected against multiplicity due to interim analyses, because of the alpha- and beta-spending rules described in the preceding section.

The overall type 1 error rate for the study will be protected against multiplicity due to multiple doses by using a step-down, or gatekeeper, procedure. The statistical significance of the difference in response between the 3.5 mg RO7049665 group and the placebo group will be assessed if and only if the corresponding difference between the 7.5 mg RO7049665 and placebo has already been shown to be statistically significant.

The study has a single primary endpoint, corresponding to the single primary estimand. All other endpoints are secondary or exploratory. Therefore, no adjustment to nominal p-values will be made to protect the overall type 1 error rate for the study against multiplicity of endpoints.

9.4 ANALYSES SETS

For purposes of analysis, the following analysis sets are defined in [Table 10](#).

Table 10 Analysis Sets

Analysis set	Description
Intent-to-treat	All randomized participants will be included in the intent-to-treat analysis set.
Safety	All participants randomized to study treatment and who received at least one dose of the study treatment, whether prematurely withdrawn from the study or not, will be included in the safety analysis.
Immunogenicity	Participants who had at least one pre-dose or at least one postdose ADA assessment will be included and analyzed according to the treatment they actually received or were allocated to receive. The relationship between ADA status and safety, efficacy, PK, and biomarker endpoints will be analyzed and reported descriptively via subgroup analyses.
PK	Participants who had at least one pre-dose or at least one evaluable postdose PK sample will be included and analyzed according to the treatment they actually received.

Note: The analysis set for the primary estimand is defined by the estimand itself. However, unless there are any participants who are misdiagnosed and who subsequently enter the study (or other unlikely protocol violations), the intent-to-treat analysis set will be identical to the population for the primary estimand.

9.5 STATISTICAL ANALYSES

9.5.1 Demographics and Baseline Characteristics

Summaries for categorical baseline variables will include counts and frequencies. Summaries for continuous baseline variables will include counts, means, and standard deviations. Participants in the ITT analysis set will contribute to baseline summaries.

For each variable, the “baseline value” will be the last non-missing value obtained prior to the first administration of study treatment.

9.5.2 Efficacy and Pharmacodynamic Analyses

9.5.2.1 Primary Estimand

The hazard ratio will be derived from a Cox proportional hazards model for time until relapse with fixed effects for treatment arm, sex, and CCS use, expressed as equivalent prednisolone dose. The raw and median unbiased point estimates for the HR will be

presented together with associated confidence intervals and p-value. The estimated 6-month relapse rates for each arm will be presented, together with associated confidence intervals. Kaplan-Meier curves and the associated confidence intervals will be graphed.

Refer to Sections 3.1.3 and 8.1 for definitions of censoring and relapse.

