2.3 BENEFIT/RISK ASSESSMENT

As mentioned in Section 2.2.1, AIH is a chronic autoimmune disease of unknown cause, characterized by continuing hepatocellular inflammation and necrosis; it has a tendency to progress to cirrhosis. Some patients go on to develop signs and symptoms of chronic liver disease, while others rapidly progress to acute liver failure, as marked by coagulopathy and jaundice ([Wolf DC, 2019](#)). There is no registered treatment for AIH. SoC is CCS, possibly with the addition of NSIs such as, but not limited to, azathioprine (AZA), 6-mercaptopurine (6-MP) mycophenolate-mofetil (MMF) methotrexate, cyclosporine, or tacrolimus. While the vast majority of patients are responsive to CCSs, 80% of patients relapse when the CCS and /or immunosuppressive treatment is withdrawn ([van Gerven NM et al. 2013](#)). Untreated AIH has a high mortality rate due to the development of liver cirrhosis. Thus, most patients with AIH require lifelong CCS and/or immunosuppressant treatment and suffer from the side effects of chronic treatment, including osteoporosis (particularly worrisome, as AIH is common in young women), skin effects, depression, diabetes and metabolic syndrome, infection risk, etc.

The hallmark laboratory findings in AIH are elevated liver enzymes (notably ALT) and elevated serum Ig levels, primarily IgG. ALT and IgG are also the recognized disease activity markers, and the treatment goal is normalization of these two markers (known as "biochemical remission"). In most patients, this can be achieved quickly by induction of high-dose CCS therapy followed by the addition of NSIs. After response to induction therapy, CCS dose is reduced in a stepwise fashion. Complete withdrawal of immunosuppressive therapy is tried after approximately 2 years of stable remission ([EASL, 2015](#)). However, it is rarely successful; > 80% of patients require re-instigation of CCS treatment ([van Gerven NM et al. 2013](#)). Patients who relapse twice usually need to stay on immunosuppressive treatment for the rest of their life ([EASL, 2015](#)).

RO7049665 represents a potential novel therapy for AIH aiming at long-term, CCS-free remission.

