3.1.4 Summary Measure

The summary measure used to assess the effect of RO7049665 will be the hazard ratio for time to relapse between the relevant RO7049665 group and the SoC group, as

calculated by a Cox proportional hazards model with terms for treatment arm, sex, and prednisolone-equivalent CCS dose at baseline. If inclusion of any model term leads to model instability, then the terms included in the model may be modified.

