16. T or B cell-depleting therapy (e.g., rituximab) within the last 12 months or T- or B-cell number below normal due to depleting therapy.

Prior/Concurrent Clinical Study Experience

17. Leukocyte apheresis within 12 weeks of screening.
18. Donation of blood or blood products in excess of 500 mL within 3 months prior to screening.
19. Exposure to any investigational treatment within 6 months prior to Day 1.

Laboratory Abnormalities

20. Abnormal hematologic values:
 - Anemia (hemoglobin < 9 g/dL)
 - Leukocytosis (white blood cells $\geq 2 \times$ upper limit of normal [ULN])
 - Thrombocytopenia (platelet count < 100,000/ μ L)
 - Thrombocytosis (platelet count $\geq 2 \times$ ULN)
 - Eosinophilia (eosinophil count $\geq 2 \times$ ULN)
21. Abnormal hepatic enzyme or hepatic function values:
 - ALT, AST, or alkaline phosphatase, above normal range
 - Total bilirubin $\geq 2 \times$ ULN
 - International normalized ratio (INR) ≥ 1.7
 - Albumin < 3 g/dL
22. Abnormal biochemistry values:
 - IgG above normal range

Other Exclusions

23. History of regular alcohol consumption within 2 months of screening defined as:
An average weekly intake of > 14 drinks for men or > 7 drinks for women. One drink is equivalent to 12 g of alcohol: 12 ounces (360 mL) of beer, 5 ounces (150 mL) of wine, or 1.5 ounces (45 mL) of 80 proof distilled spirits (equivalent to 40 vol%).
24. Any suspicion or history of illicit drug use.

25. Patients under judicial supervision, guardianship, or curatorship.

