9.2 SAMPLE SIZE DETERMINATION

The sample size for this study is based on independent pairwise comparisons of each RO7049665 group—i.e., high dose (7.5 mg) and low dose (3.5 mg) with placebo. The total sample size required is obtained by multiplying the appropriate per-group size by three. Methods for the control of the family-wise error rate are described both in this section and in Section 9.3.

The reference treatment effect is 0.272. The study will use an overall one-sided type 1 error rate (significance level) of 2.5%. A power of 90% against the reference treatment effect is required.

There will be one opportunity to stop for success before the end of the study, at 50% information. An O'Brien-Fleming-like alpha-spending rule will preserve the type 1 error rate. The success boundary will be binding.

There will be two opportunities to stop for futility before the end of the study: once at 25% information (i.e., when 25% of the maximum number of events have occurred) and once at 50% information (i.e. when 50% of the maximum number of events have occurred). A Pocock-like beta-spending rule will preserve power of the study. The futility boundary will be non-binding.

If the proportional hazards assumption holds, these assumptions imply that 29.1 events (i.e., 30 events for all practical purposes) in the placebo and 7.5 mg RO7049665 arms combined are required to achieve the desired power and significance levels.

Under the assumption that recruitment to the study will take approximately 19 months, that sites will be activated at uniform rate for six months, after which recruitment will plateau, and that follow-up should continue for at most 6 months after the last patient to enter the study is randomized, then recruitment of 28 participants per arm will generate the required number of events.

Table 9 Summary of the Group Sequential Design

Stage	Interim 1	Interim 2	End of study
Information rate	25%	50%	100%
Efficacy boundary (z-value scale)	∞	2.963	1.969
Futility boundary (z-value scale)	-0.046	0.738	
Number of subjects ^{a,c}	31	47	56
Cumulative number of events ^a	7.3	14.5	29.1
Analysis time ^{b,c}	11.7	16.3	25.0
Cumulative alpha spent	<0.0001	0.0015	0.025
Cumulative power	<0.0001	0.3159	0.9000
One-sided local significance level	N/A	0.0015	0.0245 ^d
Efficacy boundary (t)	N/A	0.211	0.482
Futility boundary (t)	1.035	0.679	
Overall exit probability (under H0)	0.4815	0.3136	
Exit probability for efficacy (under H0)	<0.0001	0.0015	

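### Adding baseline IgG and ALT to the primary Cox model would be a nearly free, conditional gain in power; the planned 90% stands without it

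*Combined protocol and SAP*

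**What the plan says.** Section 9.5.2.1 specifies a "Cox proportional hazards model for time until relapse with fixed effects for treatment arm, sex, and CCS use, expressed as equivalent prednisolone dose". Section 3.1.4 agrees: "terms for treatment arm, sex, and prednisolone-equivalent CCS dose at baseline". The only route to a different set of terms is in Section 3.1.4: "If inclusion of any model term leads to model instability, then the terms included in the model may be modified". None of the sensitivity analyses in Section 3.1.5 adjusts for baseline ALT or IgG, and no reason is given for leaving them out.

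Section 2.3 says that "ALT and IgG are also the recognized disease activity markers". Table 8 in Section 8.1 defines relapse by rises in these two values relative to ULN. Section 5.2 excludes anyone whose ALT is above the normal range and, separately, anyone with "IgG above normal range".

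Both tests belong to the blood chemistry panel (Appendix 4), which is drawn at screening and on Day 1 (Table 1). Section 8.1 has them assessed centrally, Section 9.5.1 defines the baseline value, and Section 9.5.2.2 already tabulates both relative to ULN.

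**The concern.** Relapse in Table 8 is a threshold crossing, so a participant's starting distance from the threshold could plausibly predict time to relapse. The case is clearest for IgG, where the entry ceiling of 1 x ULN is also the level that starts the first retest. ALT has further to go: it must reach 2 x ULN.

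The primary comparison rests on about 30 events in two arms of 28. In a trial of that size, leaving out a strongly prognostic covariate pulls the estimated hazard ratio towards 1, compared with the hazard ratio given that covariate, and costs power. Because terms may change only for instability, a baseline IgG imbalance seen after unblinding could be handled only post hoc. The model does carry sex, which is not a stratification factor and for which the documents give no prognostic reason.

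**Working it through.** **1. The plan's own figure.** Inputs are from Sections 9.1 and 9.2: six-month relapse of 45% and 15%, one-sided 2.5%, power 90%, 1:1 in the pair.

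- Hazard ratio: ln(0.85)/ln(0.55) = 0.2718. Means: 6/0.598 = 10.0 and 6/0.1625 = 36.9 months. All match.
- Fixed design (Schoenfeld): 4 x (1.960 + 1.282)^2 / ln(0.272)^2 = 24.8 events.
- Group sequential inflation for the stated alpha and beta spending with non-binding futility: 1.174. Then 24.8 x 1.174 = 29.1 events. The boundaries (2.963, 1.969, -0.046, 0.738) also match Table 9.

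So the sample size is correct on its own inputs and does not rely on covariate adjustment.

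**2. What 0.272 stands for.** It comes from relapse rates for whole arms, averaged over all baseline values. A fair comparison of models must therefore keep the arm-level rates at 45% and 15% whatever strength is assumed for the markers.

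**3. Simulation on that basis.** There are 28 per arm, and the final test is against z = 1.969 at about 30 events in the pair. IgG and ALT are two standardised markers of equal strength. The strength is an assumption: log hazard ratio per SD of 0, 0.3 or 0.5 each, that is hazard ratios of 1.00, 1.35 or 1.65. The current model (arm, sex, dose) is set against the same model plus both markers.

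| Log HR per SD, each marker | Power at planned effect: current | plus both | Change | Power at 75% of planned log HR: current | plus both | Change |
|---|---|---|---|---|---|---|
| 0 | 91.9% | 91.2% | -0.7 | 73.3% | 72.7% | -0.6 |
| 0.3 | 92.0% | 93.8% | +1.8 | 70.3% | 74.1% | +3.8 |
| 0.5 | 89.6% | 94.7% | +5.1 | 65.5% | 77.2% | +11.7 |

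The 75% case corresponds to a hazard ratio of 0.272^0.75 = 0.377. Under the null, rejection was 2.4-3.7% for the current model and 2.7-3.7% with both markers, against a nominal 2.45%. Each entry carries simulation error of roughly a point.

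**4. Cost in terms.** Two more terms take 30 events from 30/3 = 10 per term to 30/5 = 6. At the second interim, the 14.5 events in Table 9 give 14.5/3 = 4.8 per term now and 14.5/5 = 2.9 with both markers.

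**The case against.** The strongest reply is that nothing planned is lost. Section 9.2 asks for 90% power, and the current model gives 89.6-92.0% across the assumed range. This stands, and it is why the point is an improvement and not a correction.

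The prognostic strength is unknown. Entry requires biochemical remission with ALT and IgG not above normal, which narrows both covariates, and at weak strength the gain is a point or two. This also stands.

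The threshold argument is looser than it first looks. In Table 8, IgG between 1 and 1.5 x ULN becomes relapse only if it is still raised at the 14-day check and again 14 days later, or if it reaches 1.5 x ULN. The synopsis gives only IgG above 1.5 x ULN as its example of an event. AIH-related steroid increase or reintroduction and treatment-related discontinuation also count as events (Table 6) without any threshold being crossed. This weakens the expected association but does not remove it.

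Two stronger readings are tempting. A reader might infer that the trial is underpowered as written. If 0.272 is imposed as the hazard ratio given the markers, the current model's power does fall, to 86.1% at a hazard ratio of 1.5 per SD each and 73.4% at 2.0. But the unadjusted median hazard ratio then drifts from 0.26 to 0.36, which departs from the arm-level rates in Section 9.1. The documents do not support that reading.

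A reader might also infer that sex should make way for the markers. With one marker at 0.5 per SD, power is 93.7% whether sex is kept or dropped, so removing it buys nothing. Sex is also a matching variable in the imputation analysis of Section 3.1.5.

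Finally, attenuation without the markers is not bias. The two models estimate different conditional hazard ratios, and chance imbalance under randomization is already covered by the type 1 error.

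**Conclusion.** The omission is real, consistent across Sections 3.1.4 and 9.5.2.1, and unexplained. It does not invalidate the test or the stated 90% power. Adding both markers is worth about -1 to +5 points at the planned effect, and about -1 to +12 points if the true log hazard ratio is 75% of that planned, for strengths from 0 to 0.5 per SD each. The asymmetry favours adding them: under 1 point at risk if they are uninformative, several points to gain if they are moderately prognostic, and the larger gain where the drug works less well than hoped.

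This rests on an assumed prognostic strength, on two markers of equal strength, and on the final boundary alone. Model behaviour at the interims, where events per term are few, was not examined.

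**What to change.** Before unblinding, and preferably before the first interim so that one model serves every look, amend Sections 3.1.4 and 9.5.2.1. Add baseline IgG/ULN and ALT/ULN as continuous terms, using the last central value before first dose, beside treatment arm, the steroid term and sex. State that the resulting hazard ratio is conditional on these covariates. If the sponsor prefers to keep the present primary model, the minimum is to pre-specify the adjusted model as a sensitivity analysis or give the reason for leaving the markers out.

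The cost is wording in two sections, with no new data. The downsides are small: up to two more terms on about 30 events, for which the instability clause in Section 3.1.4 already provides, and a summary measure whose conditioning set has changed and must be described as such.

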9.5.2.2 Secondary Endpoints

No formal hypothesis testing will be conducted for any secondary endpoint.

Changes in ALT and IgG

Values of ALT and IgG (both absolute and relative to ULN) will be plotted over time, grouped by treatment arm. Values (both absolute and relative to ULN) and changes from baseline will be tabulated.

For the safety analyses, see Section 9.5.3.

9.5.2.3 Exploratory Endpoints

Clinical Outcome Assessment

Absolute values and changes from baseline for PRO data will be tabulated by visit and treatment group. Where appropriate, both the overall and individual domain scores will be summarized (see Section 8.1.1 for further details).

Auto-antibodies

Absolute values and changes from baseline will be tabulated by visit and treatment group.

- Titers of auto-antibodies specific for type 1, 2, or 3 AIH.
- Titers for ANAs and/or anti-smooth muscle antibodies.

Cytokines

Absolute values and changes from baseline of inflammatory and anti-inflammatory cytokines will be tabulated by visit and treatment group.

Liver-residing Regulatory T-cells

Absolute values and changes from baseline of liver-residing T_{reg} and T_{eff} cells and the T_{reg}/T_{eff} ratio will be tabulated by visit and treatment group.

Liver Fibrosis

Raw Fibroscan® results (controlled attenuation parameter [CAP] scores in dB/m and pressure readings in kPa) will be tabulated by visit and treatment group, together with derived steatosis grades and fibrosis scores.

Component laboratory test results (alpha-2-macroglobulin, haptoglobin, apolipoprotein A1, GGT, Total bilirubin, ALT, hyaluronic acid, PIIINP and TIMP-1) will be tabulated by

visit and treatment group. If calculated, derived liver fibrosis test scores will be tabulated by visit and treatment group. If at least one required laboratory test result is not available at a visit, the derived test score will also be missing: there will be no imputation of missing laboratory test results.

Liver fibrosis scores from histology will be tabulated by visit and treatment group. Other liver histology findings will be presented in listings.

IgA and IgM

Absolute values and changes from baseline of total IgA and total IgM will be tabulated by visit and treatment group.

Pharmacodynamic Markers

- Systemic T_{reg} , T_{eff} , T_{fh} , B cells, sCD25 and in tissue may be used for modeling and simulation together with efficacy parameters.
- Absolute values and changes from baseline of T_{reg} , T_{eff} , T_{fh} , and B-cell counts in peripheral blood and tissue will be plotted over time, grouped by treatment group, and tabulated by visit and treatment group.

9.5.3 Safety Analyses

All safety analyses (see [Table 11](#)) will be based on the safety analysis population grouped according to the treatment assigned at randomization (see [Table 10](#)).

Table 11 Safety Statistical Analysis Methods

Endpoint	Statistical Analysis Methods
Adverse events	
The original terms recorded on the eCRF by the Investigator for AEs will be coded by the Sponsor.
 
Adverse events will be summarized by mapped term and appropriate thesaurus level. Incidence, nature and severity of AEs, number of participants with SAEs, treatment-related SAEs, SAEs leading to discontinuation, treatment-related AEs, or AEs leading to discontinuation will be tabulated.

Clinical laboratory tests	
All clinical laboratory data will be stored on the database in the units in which they were reported. Laboratory test values will be presented in International System of Units (SI units; Système International d'Unités) by individual outputs with flagging of abnormal results. In addition, tabular summaries will be used, as appropriate. Laboratory data not reported in SI units will be converted to SI units before processing.

Vital signs	
Vital signs data and weight data will be presented with flagging of values outside the normal ranges and flagging of abnormalities. In addition, tabular summaries will be used, as appropriate.

ECG data analysis	
ECG data will be presented using appropriate outputs, with flagging of values outside the normal ranges and abnormalities. In addition, tabular summaries will be used, as appropriate.

Concomitant medications	
The original terms recorded on the participants' eCRF by the Investigator for concomitant medications will be standardized by the Sponsor by utilizing a mapped term and appropriate drug dictionary level.
 
Concomitant medications will be presented using appropriate outputs.

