4.1.2 Stopping-rules Criteria

The study will stop if either of the interim analyses recommends stopping for success. If any interim recommends stopping for futility, the Sponsor's project team will make the actual decision whether to stop or continue the study. This process is mandated by the binding nature of the success boundary and the non-binding nature of the futility boundary defined in Section 9.2. Reasons for continuing the study after a futility recommendation could include, but are not limited to, an efficacy effect that is smaller than assumed in the sample size calculation but still of clinical relevance, or evidence of potential benefit not considered in the primary efficacy analysis.

The dosing in the study will be suspended if any of the conditions below occur in participants treated with RO7049665:

- Clinically manifest secondary (reactive) hypereosinophilia (HER) in > 3 participants.
- Grade 3 hypersensitivity reaction (as per National Cancer Institute Common Terminology Criteria for Adverse Events [NCI-CTCAE] v. 5.0) in > 1 participant considered related to RO7049665.
- Local ISRs leading to treatment discontinuation in > 5 participants, considered related to RO7049665.
- ADA with neutralizing potential against endogenous IL-2 in ≥ 1 participant.
- Other findings (e.g., presence of clinically manifest safety findings in treatment arms typically associated with therapeutic IL-2 doses as per aldesleukin label, other AEs or lab abnormalities) that, at the joint discretion of the Sponsor's lead clinical scientist and safety science leader, the Sponsor's IMC and the Investigators, indicate that dosing should be stopped.

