5.2 REPORTING REQUIREMENTS FOR CASES OF ACCIDENTAL OVERDOSE OR MEDICATION ERROR

Accidental overdose and medication error (hereafter collectively referred to as "special situations"), are defined as follows:

- Accidental overdose: accidental administration of a drug in a quantity that is higher than the assigned dose,
- Medication error: accidental deviation in the administration of a drug,
In some cases, a medication error may be intercepted prior to administration of the drug.

Special situations are not in themselves adverse events, but may result in adverse events. Each adverse event associated with a special situation should be recorded separately on the Adverse Event eCRF. If the associated adverse event fulfills seriousness criteria, the event should be reported to the Sponsor immediately (i.e., no more than 24 hours after learning of the event). For RO7049665/placebo, adverse events associated with special situations should be recorded as described below for each situation:

- Accidental overdose: Enter the adverse event term. Check the "Accidental overdose" and "Medication error" boxes.
- Medication error that does not qualify as an overdose: Enter the adverse event term. Check the "Medication error" box.
- Medication error that qualifies as an overdose: Enter the adverse event term. Check the "Accidental overdose" and "Medication error" boxes.

In addition, all special situations associated with RO7049665/placebo, regardless of whether they result in an adverse event, should be recorded on the Adverse Event eCRF and should be recorded as described below:

- Accidental overdose: Enter the drug name and "accidental overdose" as the event term. Check the "Accidental overdose" and "Medication error" boxes.
- Medication error that does not qualify as an overdose: Enter the name of the drug administered and a description of the error (e.g., wrong dose administered, wrong dosing schedule, incorrect route of administration, wrong drug, expired drug administered) as the event term. Check the "Medication error" box.
- Medication error that qualifies as an overdose: Enter the drug name and "accidental overdose" as the event term. Check the "Accidental overdose" and "Medication error" boxes. Enter a description of the error in the additional case details.
- Intercepted medication error: Enter the drug name and "intercepted medication error" as the event term. Check the "Medication error" box. Enter a description of the error in the additional case details.

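### Safety tables are grouped by assigned treatment, so if a participant received another arm's treatment, the resulting adverse events would be counted under the wrong arm

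*Combined protocol and SAP*

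**What the plan says.** Section 9.5.3 sets one grouping rule for every safety output: participants are "grouped according to the treatment assigned at randomization". It refers to Table 10 in Section 9.4, but the Safety row there defines membership only: "All participants randomized to study treatment and who received at least one dose of the study treatment". That row does not say in which arm a participant is counted.

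Other parts of the protocol look at what was given:

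- **PK set (Table 10):** participants with "at least one evaluable postdose PK sample will be included and analyzed according to the treatment they actually received".
- **Immunogenicity set (Table 10):** "analyzed according to the treatment they actually received or were allocated to receive". This leaves both options open, but it does mention actual treatment.
- **Suspension rules (Section 4.1.2):** "The dosing in the study will be suspended if any of the conditions below occur in participants treated with RO7049665".

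Appendix 2, Section 5.2 foresees dosing errors. Its examples of medication error are "wrong dose administered, wrong dosing schedule, incorrect route of administration, wrong drug, expired drug administered". Nowhere does the protocol provide a safety table by treatment received, or a sensitivity analysis on that basis.

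**The concern.** A safety table should show what happened to people who were exposed to a given treatment. Under the rule in Section 9.5.3, an adverse event in a placebo participant who was given RO7049665 by mistake is a placebo event. An event in a 3.5 mg participant who was given 7.5 mg is a 3.5 mg event. If drug-related events are more common on active treatment or at the higher dose, such errors pull the arms together. That direction is not conservative for safety.

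It matters here because Section 4.2.2 justifies the placebo arm partly as a means of establishing whether adverse events are drug-related, and safety and tolerability is a secondary objective in Table 5. The arms are small, so one participant is visible in an incidence table. The same participant could also appear under one arm in a PK summary and under another in the adverse event tables.

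**Working it through.** The plan gives no figure for this point, so there is nothing to reproduce. The check has two parts: whether the rule stands, and how much it could move a table.

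**Does the rule stand?** Section 9.5.3 is explicit. The Safety row of Table 10 neither repeats nor overrides it. Section 9.7 lists protocol deviations and study treatment administration, but provides no tabulation by treatment received. The as-randomised rule is therefore the operative one.

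**Inputs**

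- 28 participants per arm, 84 in total (Section 9.2). I assume that all are dosed and so belong to the safety set.
- One participant receives another arm's treatment throughout and has the event of interest.
- As randomised, x participants have the event in the assigned arm (including this one, so x ≥ 1) and y in the arm whose treatment was received (y ≥ 0).

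**Assigned arm.** As randomised, incidence is x/28. As received, it is (x − 1)/27.

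Shift = x/28 − (x − 1)/27 = (27x − 28x + 28)/756 = (28 − x)/756

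The maximum is at x = 1: 27/756 = 3.6 percentage points.

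**Received arm.** As randomised, incidence is y/28. As received, it is (y + 1)/29.

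Shift = (y + 1)/29 − y/28 = (28y + 28 − 29y)/812 = (28 − y)/812

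The maximum is at y = 0: 28/812 = 3.4 percentage points.

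Both are upper bounds. With x = 3 and y = 11 (illustrative), the shifts are 25/756 = 3.3 and 17/812 = 2.1 points.

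**Effect on the contrast.** Suppose m participants are swapped each way between placebo and 7.5 mg. The tabulated risk difference is then the true difference × (1 − 2m/28). The documents give neither adverse event risks nor an error rate, so both are assumptions here.

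| Assumed risk, placebo / 7.5 mg | No swap | One each way | Two each way |
|---|---|---|---|
| 10% / 40% | 30.0 points | 27.9 points | 25.7 points |
| 5% / 30% | 25.0 points | 23.2 points | 21.4 points |

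In the first row with one swap each way, the tabulated risks are (27 × 0.10 + 0.40)/28 = 11.1% and (27 × 0.40 + 0.10)/28 = 38.9%.

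**Could an error arise?** Table 7 gives one strength, 5.0 mg/mL, for both doses. By arithmetic this is 3.5/5.0 = 0.7 mL or 7.5/5.0 = 1.5 mL. Section 6.2 has the dose prepared by a qualified individual following the IxRS and the pharmacy manual. A preparation error is possible, but the documents give no basis for saying how likely it is.

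**The case against.** The rule is prespecified and unambiguous, and the tables it governs are descriptive. A different rule for PK is not in itself a contradiction. Doses are prepared by qualified staff, the first three are given at the study center, and home dosing is done by a nurse (Section 6). Any medication error involving study treatment is recorded on the Adverse Event eCRF even when no adverse event follows, and linked adverse events are recorded separately and flagged (Appendix 2, Section 5.2). Section 9.7 lists deviations and dosing. All of this stands: no data are lost, and a careful reader could reconstruct any case.

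A further objection also stands. Treatment is given every two weeks until relapse or study closure, so an error may well be one wrong injection in an otherwise correctly treated participant. A bare as-received rule does not say where that person belongs. If the predominant treatment decides, the event stays in the same arm as now. The change therefore needs a mixed-exposure rule as well.

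A reader might infer three stronger things that the documents do not support:

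- **That misattribution will occur, or is made likely by home dosing.** No error rate is given, and nothing shows that home administration raises the risk.
- **That the link between safety, PK and ADA data is broken.** PK data go into pooled population modelling that is reported separately (Section 9.5.4), and ADA relationships are examined by ADA-status subgroup (Section 9.5.5). Neither is shown to depend on the arm label in the adverse event tables.
- **That dosing-suspension decisions would be affected.** Section 4.1.2 counts by exposure.

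What the objections do not remove is the summary-table rule itself. Listings make a misplaced event findable, but they do not put it in the right column.

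**Conclusion.** The point holds in conditional form. If a participant receives another arm's treatment, Section 9.5.3 places the resulting adverse events under the assigned arm, out of step with the PK set and the suspension rules. This tends to dilute the drug-placebo contrast when events are more frequent on drug. The bounds of 3.6 and 3.4 percentage points rest on 28 dosed participants per arm and one participant with an event who is wholly misallocated. Typical shifts would be smaller, and with no error the shift is zero. The weakness lies in the summary tables alone. The 84 participants, 45 events, 90% power and the error control are unaffected. Severity is low. I am confident about what the text says; whether it will ever matter depends on an error rate that the documents do not give.

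**What to change.** 1. In Section 9.5.3 and in the Safety row of Table 10, state that safety data are grouped by the treatment actually received.
2. Before unblinding, specify how mixed exposure is classified. For example, a participant stays in the arm of the treatment predominantly received, and adverse events after an isolated wrong dose are tabulated or listed separately by the dose received.
3. List all participants whose received and assigned treatments differ, together with any adverse events linked to medication errors.

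The cost is a few sentences of text, including the mixed-exposure rule. Dosing and medication errors are already recorded, so no new data are needed. Settling the rule before unblinding also avoids a choice of arm made with the results in view.
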